2.4.4 Analyses of efficacy endpoints

If efficacy at the interim analysis is demonstrated for the primary endpoint of annualized rate of moderate and severe COPD exacerbations over the 52-week treatment period with an alpha as determined in [Table 9](#) (see [Section 3](#)):

- All data up to the time of the interim analysis cut-off date will be used in the inferential analyses for the event type endpoints including the primary endpoint and time to event endpoints (up to the cut-off date), and the change from baseline in pre-BD FEV1 at Week 12 endpoints (both the ITT population and the baseline FeNO ≥ 20 ppb subgroup).
- For Week 52 endpoints, only participants who have the opportunity to reach Week 52 assessments at the time of the IA cut-off date (ie, completed the Week 52 study period or would have completed had they not discontinued) will contribute to the inferential analyses for the continuous and proportion type endpoints at Week 52 and by visit.

2.4.4.1 Analysis of primary efficacy endpoint(s)

Primary efficacy variable

The primary efficacy variable is annualized rate of moderate or severe COPD exacerbations over the 52-week treatment period compared to placebo.

The following null hypothesis and alternative will be tested for dupilumab arm against placebo:

- H0: No treatment difference between the dupilumab dose regimen and placebo in annualized rate of COPD exacerbation.
- H1: There is a treatment difference between the dupilumab dose regimen and placebo in annualized rate of COPD exacerbation.

Primary statistical model (ITT analysis)

The primary analysis of the annualized rate of moderate or severe exacerbation events during the 52-week placebo-controlled treatment period is to assess the efficacy of dupilumab in an intention-to-treat setting. Adjudicated COPD exacerbation events data will be used. Patients who permanently discontinue the study medication will be encouraged to return to the clinic for all remaining study visits. If a patient stays in study until the end of 52-week treatment period, all moderate or severe exacerbation events that happen up to Visit 16 will be included in the primary analysis, regardless of if the patient is on treatment or not. And the observation duration is defined as from randomization to Visit 16 (Week 52). If a patient withdraws from study prior to the end of 52-week treatment period, all observed moderate or severe exacerbation events up to the last contact date or the end date of the planned 52-week treatment period (whichever is earlier) will be included in the analysis, and the observation duration is defined as from randomization to the last contact date or the end date of the planned 52-week treatment period whichever is earlier.

No imputation will be performed for the unobserved events that may happen after study discontinuation and up to Week 52. This estimand compares the rates of moderate or severe exacerbation for the patients randomized to the dupilumab and placebo arms, regardless of what treatment patients actually received. It assesses the benefits of the treatment policy or strategy relative to placebo.

The annualized rate of moderate or severe COPD exacerbation events will be analyzed using a negative binomial regression model. The model will include the total number of events that occurred during the 52-week planned treatment period as the response variable, with the treatment group, region (pooled country), ICS dose at baseline (high dose ICS [yes/no]), smoking status at screening (current smokers or not), baseline disease severity (as % predicted post-bronchodilator FEV₁), and number of moderate or severe COPD exacerbation events within one year prior to the study (≤ 2 , 3, or ≥ 4) as covariates. Log-transformed observation duration will be used as offset variable. The estimated annualized event rate for each treatment group and its two-sided 95% confidence intervals will be derived. The event rate ratio of the dupilumab group against placebo, its two-sided 95% confidence interval and p-value will be provided.

The rate difference between dupilumab and placebo, two-sided 95% confidence intervals of the rate difference and its p-value derived using delta method will also be provided as supportive information.

The analysis model will be built with the following sample SAS code:

```
#  
surf#jolpp1{#gdwd@hyhqw>#  
fodvv##1fv#wuw34sq#fqw|ju4q#vprnlqj#frsgqxp>#  
prgho#qxphyhqwv@wuw34sq#fqw|ju4q#1fv#vprnlqj#IHY4eo#frsgqxp#  
2riivhw@orjgxu#g1vw@qhje1q#olqn@orj#vroxwlrq>#  
uxq>#
```

If the model fails to achieve convergence, different estimation algorithms will be applied following the order: default→LAPLACE→QUAD. If the issue still exists, other handling may be considered. The adjustment will be added to the footnote of the corresponding outputs.

The gross estimated annualized event rate will also be presented by treatment group.

Mean cumulative function plot will be provided for descriptive purpose.

Primary estimand for the primary efficacy endpoint is summarized in Appendix L.

Sensitivity analysis

If patients withdraw from the study before Visit 16 (Week 52), moderate or severe exacerbation events that may occur after study discontinuation will not be observed. These patients are considered as patients with missing data on moderate or severe exacerbation. Number of patients with missing data, reasons and timing for patient withdrawals will be summarized by treatment groups. Summary statistics of selected demographic and baseline disease characteristics will be provided for patients with missing data and patients with complete data separately. In addition, the following sensitivity analyses will be conducted to assess the robustness of the conclusion based on the primary analysis.

Pattern mixture model - multiple imputation (PMM-MI)

For each patient with missing data of moderate or severe exacerbation events, individual bi-weekly event probability will be estimated using observed data with adjustment of the planned treatment group, region (pooled country), ICS dose at baseline (high dose ICS [yes/no]), smoking status at screening (current smokers or not), baseline disease severity (as % predicted post-bronchodilator FEV₁), and number of moderate or severe COPD exacerbation events within one year prior to the study (≤ 2 , 3, or ≥ 4). The total number of AECOPD moderate or severe events (on bi-weekly basis) will be calculated based on data imputed using multiple imputation.

Control-based PMM-MI

For each patient with missing data of moderate or severe exacerbation events, individual bi-weekly event probability will be estimated using observation in the placebo arms only, with adjustment of region (pooled country), ICS dose at baseline (high dose ICS [yes/no]), smoking status at screening (current smokers or not), baseline disease severity (as % predicted post-bronchodilator FEV₁), and number of moderate or severe COPD exacerbation events within one year prior to the study (≤ 2 , 3, or ≥ 4). The total number of AECOPD moderate or severe events (on bi-weekly basis) will be calculated based on data imputed using multiple imputation.

Tipping point analysis

For each patient with missing data of moderate or severe exacerbation events, the bi-weekly event will be imputed in a similar fashion as PMM-MI based on various odds values. If the patient is on dupilumab, the predicted odds will be increased; if the patient is on Placebo, the predicted odds value will be decreased. The adjusted rate will then be used to impute the number of events that

would occur during the missing observation period. A sequence of increasing/decreasing ratio will be used to generate different imputed datasets.

For each of the above methods, a negative binomial model will be fitted using each of the complete datasets composed of observed and imputed data, including the total number of observed and imputed events during the 52 weeks as the response variable, with the treatment group, region (pooled country), ICS dose at baseline (high dose ICS [yes/no]), smoking status at screening (current smokers or not), baseline disease severity (as % predicted post-bronchodilator FEV₁), and number of moderate or severe COPD exacerbation events within one year prior to the study (≤ 2 , 3, or ≥ 4) as covariates. Log transformed observation duration will be the offset variable for patients who complete the 52-Week treatment/study period, and log transformed 52 weeks will be the offset variable for patients who discontinue the study before Visit 16 (Week 52). SAS MIANALYZE procedure will be used to generate statistical inferences by combining results from the analysis with each dataset using Rubin's formula.

More details of the imputation and analyses methods are provided in Appendix K:

Subgroup analyses

To assess the consistency in treatment effects across different subgroup levels, subgroup analyses will be conducted for the primary efficacy endpoint with respect to:

- Age group (<65, ≥ 65 years; 40-64, 65-74, 75-85)
- Gender (Male, Female)
- Region
- Territory
- Race (White, Non-white)
- Ethnicity (Hispanic or Latino, Not Hispanic or Latino)
- Baseline weight (<70, ≥ 70 - <90, ≥ 90 kg; <60, ≥ 60 kg)
- Baseline BMI (<25, ≥ 25 - <30, ≥ 30 kg/m²)
- ICS high dose level at baseline (High-dose ICS, Non-high-dose ICS, No ICS)
- ICS dose level at baseline (< median, \geq median)
- Smoking status at screening (current smokers, former smokers)
- Number of moderate-or-severe COPD exacerbation events within one year prior to V1 (≤ 2 , 3, or ≥ 4)
- Number of severe COPD exacerbation events within one year prior to V1 (0, 1, ≥ 2 ; 0, ≥ 1)
- Baseline predicted post-bronchodilator FEV₁% (<50%, $\geq 50\%$)
- Baseline pre-bronchodilator FEV₁ (< median, \geq median)
- Baseline FEV₁ reversibility (<12%, $\geq 12\%$; < median, \geq median)
- Baseline fractional exhaled nitric oxide (FeNO) (<20, ≥ 20 ppb)
- Baseline eotaxin-3 (< median, \geq median)
- Baseline IgE (<100, ≥ 100 IU/ml)

- Baseline PARC (< median, \geq median)
- Baseline Fibrinogen (<350, \geq 350 mg/dL)
- Maximum eosinophils count during screening (<0.5, \geq 0.5 Giga/L)
- Emphysema ongoing at baseline (Yes, No)
- Baseline BODE (\leq 4, $>$ 4)

Treatment by subgroup interaction and its p-value will be derived from a negative binomial model. This model will include the total number of events occurring during the observation period as the response variable, with the two treatment groups, region (pooled country), ICS dose at baseline (high dose ICS [yes/no]), smoking status at screening (current smokers or not), baseline disease severity (as % predicted post-bronchodilator FEV₁), and number of moderate or severe COPD exacerbation events within one year prior to the study (\leq 2, 3, or \geq 4), subgroup (if different than the aforementioned covariates) and treatment by subgroup interaction as covariates.

Log transformed observation duration will be the offset variable. Summary statistics of moderate or severe exacerbations will be provided within each subgroup. Forest plot of relative risks and corresponding CIs and forest plot of risk differences and corresponding CIs comparing dupilumab dose group vs. placebo for the subgroups will be provided.

2.4.4.2 Analyses of key secondary efficacy endpoints

2.4.4.2.1 Analysis of the change from baseline in pre-bronchodilator(pre-BD) FEV₁ at Week 12 for dupilumab versus placebo

The change from baseline in pre-bronchodilator FEV₁ at Week 12 will be analyzed using mixed-effect model with repeated measures (MMRM). The analysis will be performed in the full ITT population and also in the baseline FeNO \geq 20 ppb subgroup. The model will include change from baseline in FEV₁ values up to Week 12 as response variables, and factors for treatment group, age, sex, height, region (pooled country), ICS dose at baseline (high dose ICS [yes/no]), smoking status at screening (current smokers or not), visit, treatment-by-visit interaction, baseline pre-bronchodilator FEV₁, and FEV₁ baseline-by-visit interaction as covariates. An unstructured correlation matrix will be used to model the within-patient errors. Parameters will be estimated using restricted maximum likelihood method using the Newton-Raphson algorithm. The least square (LS) mean of the change in pre-bronchodilator FEV₁ of each treatment group, difference in the LS mean changes between the dupilumab group and placebo, the corresponding 95% CI of the differences and p-values will be provided. For patients who discontinued the study treatment, off-treatment FEV₁ values will be included in the analysis.

Primary estimand for the key secondary efficacy endpoints is summarized in Appendix L.

Subgroup analyses

To assess the consistency treatment effects across the subgroup levels, subgroup analyses will be conducted for the change from baseline in pre-BD FEV₁ at Week 12 with the same set of subgroups as defined for the annualized rate of moderate or severe AECOPD events in [Section 2.4.4.1](#).

Treatment-by-subgroup interaction at Week 12 and its p-value will be derived from a MMRM model. The model will include change from baseline in pre-BD FEV₁ values up to Week 12 as response variables, and treatment, age, sex, height, region (pooled country), ICS dose at baseline (high dose ICS [yes/no]), smoking status at screening (current smokers or not), visit, treatment-by-visit interaction, baseline pre-bronchodilator FEV₁, and FEV₁ baseline-by-visit interaction, subgroup (if different than the aforementioned covariates), subgroup-by-treatment interaction and subgroup-by-treatment-by-visit interaction as covariates. Summary statistics of change from baseline in pre-bronchodilator FEV₁ will be provided within each subgroup. Forest plot of LS mean difference and corresponding CIs for the subgroups will be provided.

Sensitivity analysis

Patients who discontinue the treatment are encouraged to follow the planned clinical visits, and all data collected after treatment discontinuation will be used in the analysis. Descriptive statistics of pre-BD FEV₁ by visit up to Week 12 will be summarized for patients with some missing data and patients with complete data up to Week 12 separately. Number of patients with missing pre-BD FEV₁, reasons and timing for missing pre-BD FEV₁ will be summarized by treatment groups. In addition, following sensitivity analyses will be conducted to assess the robustness of the conclusion of the main model using the full ITT population:

Pattern mixture model-multiple imputation (PMM-MI)

Missing pre-BD FEV₁ values will be imputed multiple times with adjustment for covariates including treatment groups, age, sex, height, region (pooled country), ICS dose at baseline (high dose ICS [yes/no]), smoking status at screening (current smokers or not), and baseline pre-BD FEV₁. Each of the complete datasets will be analyzed using the ANCOVA model with change from baseline in pre-BD FEV₁ at Week 12 as the response variable, treatment, age, sex, height, region (pooled country), ICS dose at baseline (high dose ICS [yes/no]), smoking status at screening (current smokers or not), and baseline pre-BD FEV₁ value as covariates. Then the SAS MIANALYZE procedure will be used to generate statistical inference by combining results using Rubin's formula.

Tipping point analysis

First, missing values will be imputed by PMM-MI as illustrated above. The imputed values in placebo group will then be shifted by adding a sequence of positive values and the imputed values in dupilumab group will be shifted by subtracting a sequence of positive values. For each combination of the shift parameters, each of the imputed and shifted datasets will be analyzed with the ANCOVA model and their results will be combined using Rubin's formula to generate statistical inference. LS mean difference between dupilumab and placebo in change from baseline in pre-BD FEV₁ at Week 12 and the corresponding p-values will be provided for each combination of shift parameters.

More details of the imputation and analyses methods are included in Appendix K.

2.4.4.2.2 Analysis of the change from baseline in pre-bronchodilator FEV₁ and SGRQ total score and domain scores at Week 52 for dupilumab versus placebo

The change from baseline in pre-bronchodilator FEV₁ at Week 52 will be analyzed in a similar way as change from baseline in pre-bronchodilator FEV₁ at Week 12 and the model will include values up to Week 52 as response variables. The analysis will be performed in the full ITT population and also in the baseline FeNO ≥ 20 ppb subgroup.

The change from baseline in SGRQ total score and domain scores at Week 52 will be analyzed in a similar way as change in pre-bronchodilator FEV₁ at Week 52 except that the MMRM model will include the following covariates: treatment group, region (pooled country), ICS dose at baseline (high dose ICS [yes/no]), smoking status at screening (current smokers or not), visit, treatment-by-visit interaction, baseline SGRQ total score, and SGRQ baseline-by-visit interaction.

Descriptive statistics including number of patients, mean, standard error, and least squares (LS) means will be provided. In addition, difference in LS means and the corresponding 95% confidence intervals (CI) will be provided along with the p-values.

2.4.4.2.3 Analysis of proportion of patients with SGRQ improvement ≥ 4 points at Week 52 dupilumab versus placebo

The proportion of patients with SGRQ improvement ≥ 4 points at Week 52 will be analyzed using a logistic regression model. The model will include treatment group, region (pooled country), ICS dose at baseline (high dose ICS [yes/no]), smoking status at screening (current smokers or not), and baseline SGRQ total score as covariates. For patients who discontinue treatment early, data collected during the off-treatment period will be used to determine the responder/non-responder status. Patients with missing SGRQ total score at Week 52 will be considered as non-responders.

Odds ratio of being a responder comparing dupilumab to placebo will be provided along with the corresponding 95% CI and p-value. Descriptive statistics including number and percentage of responders will also be provided.

Cumulative distribution function (CDF) of change from baseline in SGRQ at Week 52 will be presented by treatment group.

2.4.4.2.4 Analysis of annualized rate of moderate or severe COPD exacerbation compared to placebo over the 52-week treatment period in the subgroup of patients with baseline FeNO ≥ 20 ppb

The annualized rate of moderate or severe COPD exacerbation compared to placebo over the 52-week treatment period in the subgroup of patients with baseline FeNO ≥ 20 ppb will be performed in the same approach as that for the primary efficacy endpoint except that the analyzed population is not the full ITT population but the subgroup of patients with baseline FeNO ≥ 20 ppb.

The estimated annualized event rate for each treatment group and its two-sided 95% confidence intervals will be derived. The event rate ratio of the dupilumab group against placebo, its two-sided 95% confidence interval and p-value will be provided.

The rate difference between dupilumab and placebo, two-sided 95% confidence intervals of the rate difference and its p-value derived using delta method will also be provided as supportive information.

Mean cumulative function plot will be provided for descriptive purpose.

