Scores by dimension are calculated for three domains: Symptoms, Activity and Impacts (Psychosocial) as well as a total score. Global and domain scores range from 0 to 100, with 100 representing the worst possible health status and 0 indicating the best possible health status. See St. George's Respiratory Questionnaire manual Version 2.3 page 8-13 (Appendix C) for the scoring algorithm.

The first part ("Symptoms") evaluates symptomatology, including frequency and severity of cough, sputum production, wheeze, breathlessness and the duration and frequency of attacks of breathlessness or wheeze. The second part has two components: "Activity" and "Impacts". The "Activity" section addresses disturbances to patients' daily physical activities. The "Impacts" section covers a range of effects that chest troubles may have on patients' daily life and psychosocial functions (eg, daily life activities and functioning, employment, physical functioning, emotional impact, stigmatization, and patients' perceptions when treated). The recall period of the questionnaire is over the past 4 weeks.

Psychometric testing has demonstrated its repeatability, reliability and validity. Sensitivity has been demonstrated in clinical trials. A minimum change in score of 4 units was established as clinically relevant after patient and clinician testing (4, 5). The SGRQ has been used in a range of disease groups including asthma, COPD and bronchiectasis.

SGRQ is assessed at Visit 2 (Week 0), Visit 4 (Week 4), Visit 6 (Week 12), Visit 9 (Week 24), Visit 12 (Week 36), Visit 16 (Week 52), and Visit 19 (Week 64).

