2.4.4.3 Multiplicity issues

Multiplicity is considered for performing an interim analysis and for testing multiple endpoints. The overall Type-I error rate will be controlled at the two-sided 0.05 level.

An interim analysis will be performed using the Kim-DeMets (9) spending function when the information fraction is ≥ 0.92 based on follow-up time for the primary endpoint of annualized rate of moderate or severe COPD exacerbations over 52-week treatment period (see [Section 3](#)).

A hierarchical testing procedure will be used for testing primary, key secondary and other endpoints. If the primary endpoint does not demonstrate efficacy at this interim analysis then the study will remain blinded and the primary endpoint will be retested at the 52-week final analysis time point with an $\alpha=0.049$. If the primary endpoint demonstrates efficacy at this interim analysis based on the alpha allocated, then the rest of the multiplicity-controlled endpoints will be tested with $\alpha=0.05$. The comparisons will be tested based on the hierarchical order below.

1) Primary efficacy endpoints:

- Annualized rate of moderate or severe COPD exacerbations over the 52-week treatment period compared to placebo.

2) Secondary/exploratory efficacy endpoints:

- Change in pre-bronchodilator FEV₁ from baseline to Week 12 compared to placebo
- Change in pre-bronchodilator FEV₁ from baseline to Week 52 compared to placebo
- Change in pre-bronchodilator FEV₁ from baseline to Week 12 compared to placebo in the subgroup of patients with baseline FeNO ≥ 20 ppb
- Change in pre-bronchodilator FEV₁ from baseline to Week 52 compared to placebo in the subgroup of patients with baseline FeNO ≥ 20 ppb
- Change from baseline to Week 52 in SGRQ total score compared to placebo
- Proportion of patients with SGRQ improvement ≥ 4 points at Week 52 compared to placebo
- Change in E-RS COPD total score from baseline to Week 52 compared to placebo
- Annualized rate of moderate or severe COPD exacerbation compared to placebo over the 52-week treatment period in the subgroup of patients with baseline FeNO ≥ 20 ppb

The study is considered positive when the primary endpoint achieves statistical significance.

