- EQ-5D-5L single index and EQ visual analog scale score will be analyzed using MMRM model with the following covariates: treatment group, region (pooled country), ICS dose at baseline (high dose ICS [yes/no]), smoking status at screening (current smokers or not), visit, treatment-by-visit interaction, baseline EQ-5D-5L single index (or EQ visual analog scale score), and corresponding baseline-by-visit interaction. Descriptive statistics including number of patients, mean, standard error, and least squares (LS) means will be provided. In addition, difference in LS means and the corresponding 95% confidence intervals (CI) will be provided.

2.4.4.5.2 Analyses of time to first severe COPD exacerbation compared to placebo during the 52-week treatment period

The time to first severe COPD exacerbation will be analyzed using the same approach as that for the analyses of time to first moderate or severe COPD exacerbation compared to placebo during the 52-week treatment period. Hazard ratio and corresponding 95% CI and p values will be estimated for dupilumab versus placebo. The Kaplan-Meier method will be used to derive the probabilities that a patient would experience an event up to specific timepoints for each treatment group. Kaplan-Meier curves will be generated; point probabilities will be calculated. Interval estimates will be calculated using 95% point wise confidence intervals.

2.4.4.5.3 Analyses of COPD exacerbation utilizing the Exacerbations of Chronic Pulmonary Disease Tool (EXACT)

COPD exacerbation will be derived using EXACT method as specified in the Exacerbations of Chronic Pulmonary Disease Tool (EXACT) Patient-Reported Outcome (PRO) User Manual-Scoring guide (Version 8.0), March 2016.

The annualized event rate of COPD exacerbations assessed by the EXACT over 52 weeks (a tertiary/exploratory endpoint) will be analyzed in the same way as the primary analysis for the

annualized rate of moderate or severe COPD exacerbation events but based on exacerbation defined by EXACT method instead of the adjudicated data of AECOPD page in eCRF. The estimated event rate for each treatment group and its two-sided 95% confidence intervals will be provided. The event rate ratio of dupilumab against placebo, two-sided 95% confidence intervals of the rate ratio will also be provided.

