Secondary endpoint – Continuous	Change from baseline in FEV ₁ at Week 12 Change from baseline in FEV ₁ at Week 52 Change from baseline in SGRQ at Week 52 Change from baseline in E-RS at Week 52 ^b	ITT (For FEV ₁ endpoints, also patients with baseline FeNO ≥ 20 ppb)	
The intercurrent events will be handled as follows:
 
 Discontinuing the study intervention prior to Week 12 or Week 52: all data collected after discontinuation will be used in the analysis (treatment policy strategy). 
In addition, the missing data imputation rules are as follows:
 
 Missing data will be imputed latently by MMRM based on missing at random assumption 	MMRM model using change from baseline in corresponding endpoint values up to corresponding weeks as response variables, and factors for treatment group, age, sex, height (age, sex and height are only included for spirometry endpoints analyses), region (pooled country), ICS dose at baseline, smoking status at screening, visit, treatment-by-visit interaction, baseline value of the endpoint, and baseline-by-visit interaction as covariates.

Endpoint Category	Estimands			
	Endpoint(s) ^a	Population	Intercurrent event(s) handling strategy and missing data handling	Population-level summary
Secondary endpoint – Proportion	Proportion of SGRQ improvement (≥ 4 points) at Week 52.	ITT	
The intercurrent events will be handled as follows:
 
 Discontinuation of study intervention prior to Week 52: Off-study intervention data will be included in the analysis (treatment policy strategy). 
In addition, the missing data imputation rules are as follows:
 
 Having missing data at Week 52: Participants will be considered as non-responders. 	Logistic regression model, with treatment group, region (pooled country), ICS dose at baseline, smoking status at screening, and baseline SGRQ total score as covariates
Secondary objective: To evaluate the effect of dupilumab on moderate and severe COPD exacerbations				

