Secondary endpoint – Time-to-event	Time to AECOPD exacerbation events during the 52-week treatment period	ITT	
The intercurrent events will be handled as follows:
 
 Discontinuation of study intervention before Week 52: Off-study intervention data up to Week 52 will be included in the analysis (treatment policy strategy). 
In addition, the missing data imputation rules are as follows:
 
 Discontinuing the study follow-up before Week 52: Analyses will be censored at the time of study discontinuation 	Cox proportional hazards model using the time to the first event as the dependent variable, and treatment group, region (pooled country), ICS dose at baseline, smoking status at screening, baseline disease severity, and number of moderate or severe COPD exacerbation events within one year prior to the study as covariates

a Additional secondary objectives/endpoints are not included in this table but would be handled with a similar strategy as the endpoint type (ie, Continuous, proportion, event, time-to-event) at other weeks.

b Exploratory endpoint

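### The SGRQ domain-score models name the baseline total score and omit the domain's own baseline, at a small cost in precision

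*SAP*

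**What the plan says.** SAP 2.1.3.2.1 defines four SGRQ scores: "Scores by dimension are calculated for three domains: Symptoms, Activity and Impacts (Psychosocial) as well as a total score".

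SAP 2.4.4.2.2 covers all of them in one sentence: "The change from baseline in SGRQ total score and domain scores at Week 52 will be analyzed in a similar way as change" in FEV₁ at Week 52. It then replaces the FEV₁ covariates with a single list that ends: "baseline SGRQ total score, and SGRQ baseline-by-visit interaction". No sentence substitutes a domain's own baseline when the outcome is a domain score. The section goes on to promise LS mean differences with 95% confidence intervals and p-values.

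Appendix L, in its row for continuous secondary endpoints, gives the covariates as "baseline value of the endpoint, and baseline-by-visit interaction as covariates". The SGRQ entry in that row reads only "Change from baseline in SGRQ at Week 52". Footnote a adds: "Additional secondary objectives/endpoints are not included in this table but would be handled with a similar strategy as the endpoint type".

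The continuous SGRQ item in the testing order of SAP 2.4.4.3 is "Change from baseline to Week 52 in SGRQ total score compared to placebo". Domain scores do not appear there, nor in the endpoint lists of SAP 2.1.3.

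**The concern.** In a change-from-baseline analysis, the covariate that matters most is usually the baseline of the variable being analysed, because regression to the mean ties the change to that starting value. The baseline total score is related to each domain baseline but is only a proxy for it. With the proxy alone, part of the variation that the domain baseline would explain stays in the residual.

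The stake is the width of the intervals for three supportive outcomes. There is also a programming question: someone following 2.4.4.2.2 literally and someone following the convention used elsewhere in the SAP would fit different models to the same domain data. That is better settled before unblinded results exist.

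**Working it through.** **Texts side by side.**

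- Protocol 9.4.1 (Table 9) gives the same SGRQ covariate list, for the total score only. The SAP sentence extends it to domain scores, and the list is unchanged.
- For the other spirometry parameters, the same protocol table says that each parameter's own baseline takes the place of baseline pre-bronchodilator FEV₁.
- For the two EQ-5D-5L scores, SAP 2.4.4.5.1 names "baseline EQ-5D-5L single index (or EQ visual analog scale score), and corresponding baseline-by-visit interaction", so each score is adjusted for its own baseline. The BODE model in that section does likewise.
- Appendix L uses the endpoint's own baseline. For the SGRQ total score this agrees with 2.4.4.2.2, because the baseline total score is that endpoint's baseline.

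The domain-score models are therefore the exception to a pattern.

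**Size.** The documents give no figure for SGRQ domain precision, so there is none to reproduce. The stated 90% power with 462 patients per arm concerns the exacerbation rate and does not bear on this point.

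Take a single visit and standardise each score to unit variance. Let *r* be the correlation of a domain's baseline with its Week 52 value, and *q* the correlation of the domain baseline with the total baseline. Suppose the total baseline says nothing about the Week 52 domain score beyond what the domain baseline says, so that its correlation with the Week 52 domain score is *rq*. The documents give neither *r* nor *q*; the ranges below are assumptions.

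- Variance of the change: 2(1 − r).
- Covariance of the change with the domain baseline: −(1 − r). Residual variance with the domain's own baseline: 2(1 − r) − (1 − r)² = 1 − r².
- Covariance of the change with the total baseline: rq − q = −q(1 − r). Residual variance with the total baseline: 2(1 − r) − q²(1 − r)².

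| r | q | Own baseline | Total baseline | Variance ratio | Interval width |
|---|---|---|---|---|---|
| 0.7 | 0.9 | 0.51 | 0.60 − 0.0729 = 0.5271 | 1.034 | +1.7% |
| 0.5 | 0.9 | 0.75 | 1.00 − 0.2025 = 0.7975 | 1.063 | +3.1% |
| 0.6 | 0.8 | 0.64 | 0.80 − 0.1024 = 0.6976 | 1.090 | +4.4% |
| 0.7 | 0.7 | 0.51 | 0.60 − 0.0441 = 0.5559 | 1.090 | +4.4% |
| 0.5 | 0.7 | 0.75 | 1.00 − 0.1225 = 0.8775 | 1.170 | +8.2% |

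Interval width is the square root of the variance ratio. If all 924 patients contributed, the loss would equal analysing about 894 (924/1.034) down to 790 (924/1.17) with the domain's own baseline.

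**Checks.**

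- A wider grid, *r* from 0.5 to 0.8 and *q* from 0.6 to 0.95, gives variance ratios of 1.01 to 1.21, or intervals 0.5% to 10% wider.
- A simulation of 3,000 trials of 924 patients at r = 0.6, q = 0.8 gave a ratio of 1.11 against 1.09 from the formula. The mean error in the treatment difference was below 0.001 SD under both models, so neither is biased.
- If the total baseline does carry extra positive information on the Week 52 domain score, it correlates less with the change and the ratio rises. At r = 0.6, q = 0.8, raising the correlation of the total baseline with the Week 52 domain score from 0.48 to 0.58 moves the ratio from 1.09 to 1.17. With no correlation left between the total baseline and the change, the ratio is 2/(1 + r): 1.18 at r = 0.7 and 1.33 at r = 0.5.

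**The case against.** The strongest reply is that this is inherited shorthand and not a modelling decision. The list comes from a protocol paragraph about the total score. The interaction term speaks only of the SGRQ baseline. The paragraph models itself on FEV₁, whose own baseline is in the model, and a sensible programmer would use the domain baseline anyway. Much of this stands: the documents do not show that anyone chose the total score deliberately for the domains. But the list is introduced as the exception to the FEV₁ approach, its main effect names the total score explicitly, and nothing overrides it for domains. The wording gap remains.

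A reader might infer that 2.4.4.2.2 contradicts Appendix L. The documents do not support that. The Appendix L entry says only SGRQ, and the two places agree for the total score. Footnote a reaches further secondary endpoints, and domain scores are not listed among them. There is an inconsistency only if Appendix L is extended to outcomes it does not name.

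It is also fair to say that the size rests on correlations from outside the documents and on one visit without the other covariates, whereas the planned analysis is a multi-visit model. That limits the figures to an order of magnitude.

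**Conclusion.** The point holds as a minor one. Read as written, the three domain models omit the domain's own baseline, out of line with the convention elsewhere in the plan. The expected cost is intervals about 2% to 8% wider, under the assumed correlations (0.5 to 0.7 and 0.7 to 0.9) and the single-visit approximation in which the total baseline adds nothing beyond the domain baseline.

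Two stronger inferences should be resisted. The first is bias: randomization protects the estimate under either covariate. Chance imbalance in a domain baseline that is left partly uncorrected is the same loss of precision seen in one sample, not a second harm. The second is damage to the key secondary results. The total-score model already uses its own baseline, the responder analysis is a separate logistic model, and domain scores lie outside the testing hierarchy. No confirmatory conclusion changes.

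**What to change.** Add one sentence to SAP 2.4.4.2.2: for each SGRQ domain score, the model uses that domain's own baseline and the interaction of that baseline with visit. The baseline SGRQ total score and its interaction with visit stay in the total-score model only. It would help to name the domain scores in Appendix L, or to say there that they follow the same rule.

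The cost is an editorial change. The domain baselines come from the questionnaire already scheduled at Visit 2, so nothing new has to be collected. The sentence should be in place before database lock for the interim analysis, when Protocol 9.4 requires the SAP to be final.
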